1.0 Study Summary

Study Title	Objective Assessment of Pain Thresholds in Women with Vulvodynia
Study Design	Clinical Trial
Primary Objective	Develop annotated pain maps showing region and size of area sensitive to mechanical stimulus. The pain maps will be created by combining IR images, photographs, and clinical input, and will be correlated with patient co-morbidities.
Secondary Objective(s)	a-Determine changes in the location and size of sensitive regions following various conventional clinical interventions for vulvodynia. b-Develop a large, information-rich database of annotated pain maps from patients, and use Artificial Intelligence to identify patterns and trends.
Research Intervention(s)/ Investigational Agent(s)	Infrared imaging of the vulva and assessment of pain intensity using cotton-tipped swab.
IND/IDE #	N/A
Study Population	Women with vulvodynia and healthy controls
Sample Size	60 women (30 in each group)
Study Duration for individual participants	One day 1 hour

Study Specific Abbreviations/ Definitions	
--	--

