8.0 Inclusion and Exclusion Criteria*

8.1 *Describe the criteria that define who will be **included** in your final study sample.*

NOTE: This may be done in bullet point fashion.

Response:

Women > 18 years of age

Women seeking care for vulvar pain

Controls: Women seeking routine gynecologic care

8.2 *Describe the criteria that define who will be **excluded** from your final study sample.*

NOTE: This may be done in bullet point fashion.

Response:

Women < 18 years of age

Pregnancy

Women with vulvar or vaginal disorder other than pain

8.3 *Indicate specifically whether you will include any of the following special populations in your study using the checkboxes below.*

NOTE: Members of special populations may not be targeted for enrollment in your study unless you indicate this in your inclusion criteria.

Response:

- Adults unable to consent
- Individuals who are not yet adults (infants, children, teenagers)
- Pregnant women
- Prisoners

8.4 *Indicate whether you will include non-English speaking individuals in your study. Provide justification if you will exclude non-English speaking individuals.*

*In order to meet one of the primary ethical principles of equitable selection of subjects, non-English speaking individuals may **not** be routinely excluded from research as a matter of convenience.*

In cases where the research is of therapeutic intent or is designed to investigate areas that would necessarily require certain populations who may not speak English, the researcher is required to make efforts to recruit and include non-English speaking individuals. However, there are studies in which it would be reasonable to limit subjects to those who speak English. Some examples include pilot studies, small unfunded studies with validated instruments not available in other languages, studies with numerous questionnaires, and some non-therapeutic studies which offer no direct benefit.

Response:

Non-English speakers are not eligible for inclusion in the study. This is a non-therapeutic study which will offer no direct benefit.

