10.0 Eligibility Screening*

10.1 *Describe screening procedures for determining subjects' eligibility. Screening refers to determining if prospective participants meet inclusion and exclusion criteria.*

 *Include all relevant screening documents with your submission (e.g. screening protocol, script, questionnaire).*

Response: Exclusion criteria include pregnancy, age < 18 years, and active vulvar and vaginal disorder other than pain, to be assessed in two ways: during the recruitment interview and at the time of the exam.

N/A: There is no screening as part of this protocol.

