12.0 Procedures Involved*

12.1 Provide a description of **all research procedures or activities** being performed and when they are performed once a subject is screened and determined to be eligible. Provide as much detail as possible.

NOTE: This should serve as a blueprint for your study and include enough detail so that another investigator could pick up your protocol and replicate the research. For studies that have multiple or complex visits or procedures, consider the addition of a schedule of events table in in your response.

Response:

All procedures will be performed on the same day as screening and consent and are expected to take 30-60 minutes. An annotated pain map of the vulva will be created based on subjective assessment of pain, and thermographic imaging.

- A. Images and Thermographic readings will be taken with an infrared camera prior to any physical contact with the vulva of the patient other than by placing a calibrated paper drape circumferentially on the vulva outside of the area of interest. The drape will be calibrated to maintain pain map/image size comparison between patients.
- B. Subjective pain at several predetermined loci will be assessed with a cotton swab (standard of care) and rated on a Likert scale of 0-10. This data will be added to the thermographic map.
- C. Comparative analysis of the two measures will be performed (separate from visit). Patient demographic and health data (see table below) will be collected by direct participant interview and review of the patient's chart in Allscripts.

12.2 Describe what data will be collected.

NOTE: For studies with multiple data collection points or long-term follow up, consider the addition of a schedule or table in your response.

Response:

Patient Name

DOB

MR#

Date of Visit

Vulvar images, both plain and infrared.

Pain sensitivity data on a Likert scale of 0-10 using cotton-tipped swabs.

Status (PWD or Control)

Race

Gravida

Para

Vaginal Births

Cesarean Births

Sexually Active

Dyspareunia

Smoking

Marital Status

Education Level

Medical History

Depression

Anxiety

Fibromyalgia

Chronic Pelvic Pain

Interstitial Cystitis

Endometriosis

Irritable Bowel Syndrome

TMJ

Other

h/o yeast infections

h/o BV

h/o abuse

PWD Patients Only

Symptom Duration

Pain Map Score

Pain Diary Score

FSDS

Previous Rx (Y/N)

Previous Rx (type)

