Response: We are focusing on detecting vulvodynia alone, so we will choose patients that are otherwise healthy. Any patient with a pre-existing condition that may affect the outcome of our experiments will be excluded from the study.

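### Section 19.3 adds an open-ended health exclusion that is absent from 8.2 and 10.1 and, as worded, conflicts with correlating the pain maps with co-morbidities

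*Combined protocol and SAP*

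**What the plan says.** Section 19.3 asks how the quality of collected data will be controlled. The answer is about who may enrol. It says that the focus is on vulvodynia alone, "so we will choose patients that are otherwise healthy", and then: "Any patient with a pre-existing condition that may affect the outcome of our experiments will be excluded from the study". It gives no list of conditions, no assessor and no time point.

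The eligibility sections are shorter and more specific. Section 8.2 has three exclusions: age under 18, pregnancy, and "Women with vulvar or vaginal disorder other than pain". Section 10.1 has the same three, with the last worded as "active vulvar and vaginal disorder other than pain", and checks them at the recruitment interview and at the exam.

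The primary objective in Section 1.0 says that the pain maps "will be correlated with patient co-morbidities". Section 12.2 lists the data to be recorded, including depression, anxiety, fibromyalgia, chronic pelvic pain, "Interstitial Cystitis", endometriosis, irritable bowel syndrome, TMJ and an open category, and also "h/o yeast infections" and past BV. All of these come before the block marked "PWD Patients Only", so they are to be recorded in cases and controls.

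**The concern.** The plan gives two accounts of who is eligible. Staff who screen from 8.2 or 10.1 would enrol a woman with vulvodynia and fibromyalgia. Staff who apply 19.3 could turn her away, because she is not healthy apart from vulvodynia in the ordinary sense, and because a pain condition could plausibly affect a 0-10 pain rating.

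What is at stake is one clause of the primary objective. Correlating pain maps with co-morbidities requires women with and without them. If 19.3 is applied broadly, some or all of the women with them are gone. If it is applied case by case, those who remain depend on judgements that the plan does not define. Section 19.3 also does not say whether its patients include controls, so the two groups could be selected differently, although nothing in the text shows that this is intended.

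**Working it through.** The plan gives no figure to reproduce: there is no power analysis (19.2) and no co-morbidity frequency. The check is a comparison of the text, followed by an illustration of what the fix could cost.

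**Step 1. Where the rule stands.** Sections 8.2 and 10.1 each list three exclusions, and none covers general health or the general medical conditions in 12.2. The 19.3 rule is therefore in 0 of the 2 sections used for screening. Other rules also sit outside 8.2: 8.4 makes non-English speakers ineligible, and 5.1 requires women with a prior diagnosis to be symptomatic and untreated. Those rules are definite. The 19.3 rule is open-ended, and it collides with an objective.

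**Step 2. What each reading does to the correlation.**

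| Reading of 19.3 | Support in the text | Effect on women with 12.2 conditions |
|---|---|---|
| Broad: general health screen | First sentence of 19.3; 18.2 obtains chart access to confirm history and drugs that could bear on taking part | Some or all removed; which ones is not stated |
| Narrow: active vulvar or vaginal disorder only | 5.1 names these, for controls, as what could disturb the thermal map; 10.1 uses the same idea | None removed on account of those conditions |

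The narrow reading makes 19.3 consistent with 1.0 and 12.2, but 19.3 does not state it. The wording would still need aligning: 19.3 refers to pre-existing conditions, 10.1 to active disorder, and 8.2 uses neither qualifier, while 12.2 expects past yeast infection and BV among enrolled women.

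**Step 3. What keeping co-morbid women could cost the Section 3 comparison.** This is an illustration only. The inputs q (share of cases with a condition that shifts the measurement) and d (size of the shift in SD) are assumed; the documents give neither. Take q = 0.3 to 0.5, d = 0.5 to 1, controls unshifted, and 30 women per group (Section 1.0).

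- Shift in the case mean = q × d: 0.3 × 0.5 = 0.15 SD, to 0.5 × 1 = 0.50 SD.
- Standard error of the difference with unit SD = √(1/30 + 1/30) = 0.258 SD.
- Shift in standard errors: 0.15/0.258 = 0.6, to 0.50/0.258 = 1.9.
- Case SD ratio s = √(1 + q(1−q)d²): √1.0525 = 1.026, to √1.25 = 1.118.
- Standard error ratio = √((1 + s²)/2): √1.02625 = 1.013, to √1.125 = 1.061.

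Under these assumptions the loss of precision is small (1% to 6%). The possible shift in the case-control difference is the larger cost.

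**The case against.** The best defence is that the plan, read as a whole, points to the narrow reading. Section 12.2 records these conditions in enrolled women, the primary objective uses co-morbidities, and 5.1 names vulvar or vaginal disorder as what interferes. That 19.3 would then merely repeat 8.2 is no strong reply, since 10.1 repeats 8.2 as well. This stands as a reason not to assume the broad reading. It does not settle the matter, because the first sentence of 19.3 is wider than the 8.2 criterion and 18.2 leaves a wider health screen possible.

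A reader might infer that 19.3 bars every woman with any condition in 12.2, so that none of the 30 cases could contribute and no correlation could be estimated. The documents do not support that as a finding. The exclusion sentence is conditional on the condition affecting the outcome, and no passage says that depression, anxiety, irritable bowel syndrome or TMJ does so. It is one extreme reading.

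The rule also has a purpose. Restricting the sample to women with vulvodynia alone guards against confounding of the case-control difference, and Step 3 shows that this could matter. That stands, and it is why the fix includes an additional analysis.

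Finally, this is a pilot, and 19.1 describes no co-morbidity analysis, so better wording would not by itself specify one. That limits the consequence, but a pilot still needs a single definition of who is eligible.

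**Conclusion.** The point holds as a conflict in the text and should be fixed. An undefined exclusion in 19.3, absent from 8.2 and 10.1, is at odds as worded with the co-morbidity clause of the primary objective and with the data collected under 12.2. The effect on that clause runs from none (narrow reading) to loss of some or all of the co-morbid women (broad reading). The documents neither choose between the readings nor allow the number of women to be stated.

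The conflict does not undermine the study's main comparison. The endpoint in Section 3, thermographic evidence of inflammation in cases against controls, does not depend on the correlation.

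Confidence is high for the conflict itself, which rests on the wording alone. The figures in Step 3 rest on assumed inputs and serve only to weigh the downside of the fix.

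**What to change.** Reconcile 19.3 with 1.0, 8.2, 10.1, 12.2 and 18.2:

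- Replace the open-ended rule in 19.3 with a reference to the exclusions in 8.2 and 10.1, and use one term for the vulvar or vaginal disorder criterion throughout.
- If the sponsor wants any further exclusion, name the condition in 8.2 and 10.1 and apply it to cases and controls alike at the 10.1 screening, before images are analysed. Say in 18.2 which history or drugs bear on eligibility, or that none do beyond those criteria.
- Keep eligible the 12.2 conditions that are to be correlated, and drop from the stated correlation any that are excluded. Which conditions these are is for the sponsor to decide.
- Report the Section 3 comparison also with the 12.2 conditions taken into account, for example in a sensitivity analysis of women without them.

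The cost is a wording amendment and one further analysis. No extra patients, visits or measurements are needed, since 10.1 already sets the screening points and 12.2 already records the conditions in both groups. The downside is added spread and possible confounding from co-morbid women who stay eligible. The sensitivity analysis addresses the confounding at some loss of precision: if 30% to 50% of cases were set aside and all 30 controls kept (assumed, as in Step 3), 21 to 15 cases would remain and the standard error would rise from 0.258 SD to √(1/21 + 1/30) = 0.285 SD or √(1/15 + 1/30) = 0.316 SD.

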20.0 Confidentiality*

A. Confidentiality of Study Data

Describe the local procedures for maintenance of confidentiality of study data and any records that will be reviewed for data collection.

20.1 A. *Where and how will all data and records be stored? Include information about: password protection, encryption, physical controls, authorization of access, and separation of identifiers and data, as applicable. Include physical (e.g. paper) and electronic files.*

Response:

All study data, including images, will be maintained on a password-protected, HIPAA-compliant computer in the Department of Obstetrics and Gynecology, Jacobs School of Medicine. Data on this computer will identify patients only by a code. The key code with patient identifiers, stored as an Excel spreadsheet, will be kept in a separate, secure location on a password-protected, HIPAA-compliant computer in the Department of Obstetrics and Gynecology.

20.2 A. *How long will the data be stored?*

Response:

Indefinitely.

20.3 A. *Who will have access to the data?*

Response:

The PI and co-investigators.

20.4 A. *Who is responsible for receipt or transmission of the data?*

Response:

The PI and co-investigators.

20.5 A. *How will the data be transported?*

Response:

On a password-protected, HIPAA-compliant flash drive.

B. Confidentiality of Study Specimens

Describe the local procedures for maintenance of confidentiality of study specimens.

N/A: No specimens will be collected or analyzed in this research.
(Skip to Section 21.0)

20.6 B. Where and how will all specimens be stored? Include information about: physical controls, authorization of access, and labeling of specimens, as applicable.

Response:

20.7 B. How long will the specimens be stored?

Response:

20.8 B. Who will have access to the specimens?

Response:

20.9 B. Who is responsible for receipt or transmission of the specimens?

Response:

20.10 B. How will the specimens be transported?

Response:

21.0 Provisions to Monitor the Data to Ensure the Safety of Subjects*

N/A: This study is not enrolling subjects, or is limited to records review procedures only. This section does not apply.

NOTE: Minimal risk studies may be required to monitor subject safety if the research procedures include procedures that present unique risks to subjects that require monitoring. Some examples include: exercising to exertion, or instruments that elicit suicidality or substance abuse behavior. In such cases, N/A is not an acceptable response.

21.1 Describe the plan to periodically evaluate the data collected regarding both harms and benefits to determine whether subjects remain safe.

Response:

UB Box will be monitored to ensure that only study investigators have accessed the data files.

21.2 Describe what data are reviewed, including safety data, untoward events, and efficacy data.

Response:

NA

21.3 Describe any safety endpoints.

Response:

None.

21.4 Describe how the safety information will be collected (e.g., with case report forms, at study visits, by telephone calls with participants).

Response:

NA

21.5 Describe the frequency of safety data collection.

Response:

NA

21.6 Describe who will review the safety data.

Response:

NA

21.7 Describe the frequency or periodicity of review of cumulative safety data.

Response:

NA

21.8 Describe the statistical tests for analyzing the safety data to determine whether harm is occurring.

Response:

NA

21.9 Describe any conditions that trigger an immediate suspension of the research.

Response:

Data breach.

22.0 Withdrawal of Subjects*

N/A: This study is not enrolling subjects. This section does not apply.

22.1 *Describe anticipated circumstances under which subjects may be withdrawn from the research without their consent.*

Response:

Participants who consent but cannot complete the study procedures, if for example they have abnormal findings at the time of the exam, will be withdrawn from the study at the time of the study visit.

22.2 *Describe any procedures for orderly termination.*

NOTE: Examples may include return of study drug, exit interview with clinician. Include whether additional follow up is recommended for safety reasons for physical or emotional health.

Response:

If patient cannot complete the study at the time of the study visit, no additional procedures will be performed at that time

22.3 *Describe procedures that will be followed when subjects withdraw from the research, including retention of already collected data, and partial withdrawal from procedures with continued data collection, as applicable.*

Response:

If a patient chooses to return to complete the study procedures, her biographical and demographic data will be saved. If she cannot return, previously collected data will be destroyed for control participants and saved for affected women, since this data would be collected for the routine assessment anyway. If a participant decides to leave the research, she can contact the investigator so that the investigator can remove any personal medical information from the study records.

23.0 Risks to Subjects*

23.1 *List the reasonably foreseeable risks, discomforts, hazards, or inconveniences to the subjects related to their participation in the research. Consider physical, psychological, social, legal, and economic risks. Include a description of the probability, magnitude, duration, and reversibility of the risks.*

NOTE: Breach of confidentiality is always a risk for identifiable subject data.

Response:

There is minimal risk to subjects from participation in this study except minor discomfort from the cotton-tipped swab. There is no immediate risk to the imaging. Breach of confidentiality is a small risk of participation although every effort will be done to maintain security of PHI.

23.2 *Describe procedures performed to lessen the probability or magnitude of risks, including procedures being performed to monitor subjects for safety.*

Response: See section 20.1 for ways to mitigate the risk of breach of confidentiality.

23.3 If applicable, indicate which procedures may have risks to the subjects that are currently unforeseeable.

Response: N/A

23.4 If applicable, indicate which research procedures may have risks to an embryo or fetus should the subject be or become pregnant.

Response:

None.

NA

23.5 If applicable, describe risks to others who are not subjects.

Response:

NA

24.0 Potential Benefits to Subjects*

24.1 Describe the potential benefits that individual subjects may experience by taking part in the research. Include the probability, magnitude, and duration of the potential benefits. Indicate if there is no direct benefit.

*NOTE: Compensation **cannot** be stated as a benefit.*

Response:

There is no benefit directly to subjects for participation. Data from this study may improve the diagnosis and care of women with vulvodynia in the future.

25.0 Compensation for Research-Related Injury

N/A: The research procedures for this study do not present risk of research related injury (e.g. survey studies, records review studies). This section does not apply.

25.1 If the research procedures carry a risk of research related injury, describe the available compensation to subjects in the event that such injury should occur.

Response: There is no possibility of research-related injury.

25.2 Provide a copy of contract language, if any, relevant to compensation for research related injury.

*NOTE: If the contract is not yet approved at the time of this submission, submit the current version here. If the contract is later approved with **different language regarding research related injury**, you must modify your response here and submit an amendment to the IRB for review and approval.*

Response: N/A

26.0 Economic Burden to Subjects

26.1 *Describe any costs that subjects may be responsible for because of participation in the research.*

NOTE: Some examples include transportation or parking.

Response:

The study procedures may extend the length of time the patients are in the clinic which means more time away from work and may increase the cost of parking slightly.

N/A: This study is not enrolling subjects, or is limited to records review procedures only. This section does not apply.

27.0 Compensation for Participation

27.1 *Describe the amount and timing of any compensation to subjects, including monetary, course credit, or gift card compensation.*

Response:

Upon completion of study procedures, subjects will be given a \$25 One-Time Plastic Reward Card to compensate them for time spent and transportation costs.

N/A: This study is not enrolling subjects, or is limited to records review procedures only. This section does not apply.

N/A: There is no compensation for participation. This section does not apply.

28.0 Consent Process

28.1 *Indicate whether you will be obtaining consent.*

NOTE: This does not refer to consent documentation, but rather whether you will be obtaining permission from subjects to participate in a research study.

Consent documentation is addressed in Section 29.0.

Yes *(If yes, Provide responses to each question in this Section)*

No *(If no, Skip to Section 29.0)*

28.2 *Describe where the consent process will take place. Include steps to maximize subjects' privacy.*

Response:

Consent will be obtained in a private exam room within the Obstetrics and Gynecology suite at the Conventus Office Building, [name].

28.3 *Describe how you will ensure that subjects are provided with a sufficient period of time to consider taking part in the research study.*

NOTE: It is always a requirement that a prospective subject is given sufficient time to have their questions answered and consider their participation. See “SOP: Informed Consent Process for Research (HRP-090)” Sections 5.5 and 5.6.

Response:

Subjects will be allowed as much time as they need to review the requirements of study participation and ask to questions.

28.4 *Describe any process to ensure ongoing consent, defined as a subject’s willingness to continue participation for the duration of the research study.*

Response:

Prior to and during the exam, the investigator will verbally confirm that subject wishes to continue.

28.5 *Indicate whether you will be following “SOP: Informed Consent Process for Research (HRP-090).” Pay particular attention to Sections 5.4-5.9. If not, or if there are any exceptions or additional details to what is covered in the SOP, describe:*

- *The role of the individuals listed in the application who are involved in the consent process*
- *The time that will be devoted to the consent discussion*
- *Steps that will be taken to minimize the possibility of coercion or undue influence*
- *Steps that will be taken to ensure the subjects’ understanding*

Response:

HRP-090 will be followed.

We have reviewed and will be following “SOP: Informed Consent Process for Research (HRP-090).”

Non-English Speaking Subjects

N/A: This study will not enroll Non-English speaking subjects.
(*Skip to Section 28.8*)

28.6 *Indicate which language(s) other than English are likely to be spoken/understood by your prospective study population or their legally authorized representatives.*

NOTE: The response to this Section should correspond with your response to Section 8.4 of this protocol.

Response:

28.7 *If subjects who do not speak English will be enrolled, describe the process to ensure that the oral and written information provided to those subjects will be in that language, how you will ensure that subjects are provided with a sufficient period of time to consider taking part in the research study, and any process to ensure ongoing consent. Indicate the language that will be used by those obtaining consent.*

NOTE: Guidance is provided on “SOP: Informed Consent Process for Research (HRP-090).”

Response:

Cognitively Impaired Adults

N/A: This study will not enroll cognitively impaired adults.
(Skip to Section 28.9)

28.8 *Describe the process to determine whether an individual is capable of consent.*

Response:

Adults Unable to Consent

N/A: This study will not enroll adults unable to consent.
(Skip to Section 28.13)

When a person is not capable of consent due to cognitive impairment, a legally authorized representative should be used to provide consent (Sections 28.9 and 28.10) and, where possible, assent of the individual should also be solicited (Sections 28.11 and 28.12).

28.9 *Describe how you will identify a Legally Authorized Representative (LAR). Indicate that you have reviewed the “SOP: Legally Authorized Representatives, Children, and Guardians (HRP-013)” for research in New York State.*

NOTE: Examples of acceptable response includes: verifying the electronic medical record to determine if an LAR is recorded.

Response:

We have reviewed and will be following “SOP: Legally Authorized Representatives, Children, and Guardians (HRP-013).”

28.10 ***For research conducted outside of New York State, provide information that describes which individuals are authorized under applicable law to***

consent on behalf of a prospective subject to their participation in the research. One method of obtaining this information is to have a legal counsel or authority review your protocol along with the definition of “legally authorized representative” in “SOP: Legally Authorized Representatives, Children, and Guardians (HRP-013).”

Response:

